1 INTRODUCTION

The purpose of this Statistical Analysis Plan (SAP) is to provide a description of the statistical methods to be implemented for the analysis of data from the study with protocol number TNX-LVO-04. The SAP will be finalized prior to database lock. Any deviations from the SAP after database lock will be documented in the final Clinical Study Report (CSR).

2 STUDY OVERVIEW

2.1 Study Objectives

2.1.1 *Primary Objectives*

This study will evaluate the efficacy and safety of intermittent (weekly) levosimendan infusions in hemodynamic improvement with exercise in Pulmonary Hypertension with Heart Failure and Preserved Ejection Fraction (PH-HFpEF) subjects.

2.1.2 *Secondary Objectives*

The study will evaluate the effectiveness of intermittent (weekly) levosimendan infusions in improving the following:

- Change in Cardiac Index at rest and with exercise at Week 6
- Change in pulmonary vascular resistance (PVR) effect at rest and with exercise at Week 6
- Change in pulmonary capillary wedge pressure (PCWP) when supine and legs elevated at Week 6
- Patient global assessment (based on a six-point Likert scale) at Week 6
- Exercise duration 6-min walk test at Week 6
- Physician's Assessment of Functional Class
- Clinical Events: Death and hospitalizations
 - All cause hospitalizations
 - Hospitalizations attributed to any abnormality in cardiac and/or pulmonary status.

2.1.3 *Exploratory Objectives*

Baseline echocardiographic measurements of right ventricle (RV) and left ventricle (LV) function to predict favorable response to levosimendan therapy.

2.2 Study Design

2.2.1 *Overview*

[figure not shown]
This study will be conducted at approximately 20-25 sites in the United States. The Phase 2 study of levosimendan in PH-HFpEF subjects has been designed in two phases (Figure 1). The study will recruit male and female subjects meeting identified enrollment criteria for PH-HFpEF into the lead-in open label phase to identify “responders” to levosimendan intravenous infusion of at 0.10 µg/kg/min for 24 hours \pm 30 min. Subjects that have clinically relevant responses to levosimendan will be randomized to levosimendan or placebo (1:1) and receive intermittent (weekly) study drug infusions (Week 2-5). The first 36 subjects who demonstrate a \geq 4mmHg reduction in PCWP from baseline measured at bicycle exercise (25 watts) with no more than a 10% decrease from baseline in cardiac index will be classified as a “responder” to the

lead-in levosimendan dose and be randomized to the double-blind phase of the study. Patients who do not tolerate the initial levosimendan infusion due to excessive hypotension or tachycardia will be dropped from eligibility. In the double-blinded phase, patients will be randomized to levosimendan or placebo and receive a weekly dose of study drug intravenously at $0.075 \mu\text{g}/\text{kg}/\text{min}$ for 24 hours ± 30 min and if tolerated titrated to $0.10 \mu\text{g}/\text{kg}/\text{min}$ for 24 hours ± 30 min at Week 4. The infusion rate of study drug may be decreased or interrupted as clinically warranted if the subject has hypotension, tachycardia, or signs or symptoms consistent with hypovolemia (e.g., low systolic blood pressure [SBP], decreasing urine output with rising blood urea nitrogen [BUN] and serum creatinine) Record the time of discontinuation or down titration. Patients should be monitored closely until clinically stable. See Protocol Attachment 1 for infusion rates and instructions on dose adjustments. Patients will be evaluated Week 6 to determine the efficacy and safety of levosimendan. Randomized subjects that have not received study drug weekly through Week 5 and returned for evaluation on Week 6 will be replaced to ensure 18 subjects have completed in each study group.

If a subject terminates the study prematurely, procedures listed in the Week 6 visit should be performed as soon as possible. The RHC, echocardiogram, and 6-minute walk test (6MWT) do not need to be performed for subjects who terminate the study early. Subjects will be followed for safety for 2 weeks after early termination. A phone contact will be made with the subject at 24 hours (+ 24 hours), 7 days (+ 2 days), and 14 days (+ 2 days) post infusion by investigational site personnel to assess any new or ongoing adverse events. If a subject discontinues greater than 24 hours after their prior infusion, the 24-hour phone contact does not need to be performed and the next phone contact beginning at 7 days should be completed. The vital status of all subjects will be collected at the end of the trial, regardless of reason for discontinuation.

Refer to Protocol for the time and events schedule of the study procedures.

Figure 1: Study Design Flow Chart

2.2.2 Blinding

The blind is maintained by the use of matching placebo.

All subjects are to remain blinded until all subjects have completed the study (defined as Week 6) and the database is locked. The protocol specifies that the blind could be broken only if specific emergency treatment would be dictated by knowing the treatment status of the subject. In such cases, the investigator must contact the sponsor or designee. Please consult the Pharmacy Manual for unblinding procedures should the sponsor or designee be unavailable. The sponsor must be informed as soon as possible. The date, time, and reason for the unblinding must be documented in the appropriate section of the electronic Case Report Form (eCRF) and in the source document.

2.2.3 Sample Size Calculation and Power Considerations

The sample size was estimated for the primary comparison of levosimendan and placebo using SAS (v9.4) for windows procedure PROC POWER.

A total of 36 randomized subjects (at 1:1 levosimendan vs. placebo) will provide 80% power to detect the difference at two-sided 0.05 level, assuming a standard deviation (SD) of 5 mmHg in PCWP and a treatment difference of ≥ 4.9 mmHg.

2.3 Study Endpoints

2.3.1 Primary Efficacy Endpoint

- Change from baseline PCWP during bicycle exercise (25 watts) at Week 6

2.3.2 Secondary Efficacy Endpoints

- Change in Cardiac Index at rest and with exercise at Week 6
- Change in PVR effect at rest and with exercise at Week 6
- Change in PCWP when supine and legs elevated at Week 6
- Change in mean pulmonary artery pressure (mPAP) effect at rest and with exercise at Week 6
- Change in right atrial pressure (RAP) effect at rest and with exercise at Week 6
- Patient global assessment (based on a six-point Likert scale) at Week 6
- 6MWT at Week 6 (distance)
- Physician's Assessment of Functional Class
- Clinical Events: Death and hospitalizations

2.3.3 Exploratory Efficacy Endpoint

- Change in echo measurements of RV size and tricuspid annular plane systolic excursion (TAPSE)

2.3.4 Safety Endpoints

- Adverse Event
- Events of Special Interest
- Clinical Laboratory Evaluations
- Vital Signs
- Electrocardiogram

- Cardiac monitoring data (baseline, Week 5)

3 STATISTICAL METHODOLOGY

3.1 General Considerations

3.1.1 *Study Day*

Study day will be calculated from the date of first dose of study drug (lead-in infusion). The day of the first dose of study drug will be Day 1, and the day immediately before Day 1 will be Day -1. There will be no Day 0.

3.1.2 *Definition of Baseline*

Baseline is defined as the value obtained prior to lead-in study drug infusion on Visit 1. Note: The protocol-specified visit ‘Day 0’ will be referred to as ‘Visit 1’ for analysis purposes.

3.1.3 *Analysis Visit Windows*

Post-baseline assessments will be assigned a visit number based on the study day. Analysis visit windows will be defined as below:

- Screening: ≤ 28 Days Prior to Visit 1,
- Lead-In Visit: Visit 1/Week 1/Day 1,
- Visit 2/Week 2/Day 8: Day 2 to Day 11,
- Visit 3/Week 3/Day 15: Day 12 to Day 18,
- Interim Office Visit: Between Visit 3/Week 3 and Visit 4/Week 4,
- Visit 4/Week 4/Day 22: Day 19 to Day 25,
- Visit 5/Week 5/Day 29: Day 26 to Day 32, and
- Visit 6/Week 6/Day 36: Day 33 or later.

3.1.4 *Summary Statistics*

Categorical data will generally be summarized with counts and percentages of subjects. The denominator used for the percentage calculation will be clearly defined. Continuous data will generally be summarized with descriptive statistics including n (number of non-missing values), mean, median, standard deviation, minimum, and maximum.

3.1.5 *Handling of Dropouts and Missing Data*

In cases of missing or incomplete data (e.g. adverse event [AE] and concomitant medications), the missing component(s) will be assumed as the most conservative value possible. For example, AEs with missing start dates, but with stop dates either overlapping into the treatment period or missing, will be counted as treatment-emergent, taking the worst-case approach. When partial dates are present in the data, both a partial start date and/or a partial stop date will be evaluated to determine whether it can be conclusively established that the AE started prior to the start of study drug or ended prior to the start of study drug. If the above cannot be conclusively established based on the partial and/or present dates, then the AE will be considered as treatment-emergent. Actual data values as they appear in the original eCRF will be presented in the data listings. Missing values for other variables will not be imputed and only observed values will be used in data analyses and presentation.

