3.3.6 Study Duration and Drug Exposure

Study duration will be calculated as the date of last visit – date of first dose (lead-in phase) + 1. Study duration will be summarized with descriptive statistics by treatment assignments in the double-blind phase and in total. Additionally, study duration will be categorized according to the following categories:

- 1 to 15 days,
- 16 to 29 days, and
- >29 days.

A summary of subjects receiving the study drug will be provided by treatment assignments in the double-blind phase and in total for each visit on the Safety Analysis Set and Full Analysis Set.

The number of infusions for each subject will be summarized with counts and percentages by treatment assignments in the double-blind phase and in total on the Safety Analysis Set and Full Analysis Set.

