3.4.2 Secondary Efficacy Endpoints

The secondary efficacy analyses will be performed on the Full Analysis Set.

Analyses of hemodynamic endpoints will be performed using the same ANOVA model as the primary endpoint. Series Plots will be provided for PCWP by position and visit.

Patient global assessment (based on a six-point Likert scale) at Week 6 will be performed by a Mann-Whitney-Wilcoxon test for each of the six symptom's grade. Total score will be calculated as the sum of all 6 scores for the subjects with all 6 scores available.

6MWT exercise distance at Week 6 will be tested using the same ANOVA model as the primary endpoint.

Physician's assessment of New York Heart Association (NYHA) functional class (Class I to IV) will be summarized at each time point by treatment group as a shift table from baseline to post-baseline time point. Percentages will be based on the number of subjects with both a baseline and post-baseline (at the specific time point) assessment. The treatment difference of physician's assessment of functional class at Week 6 will be tested using the two-sided Pearson's chi-squared test.

The incidence of death and hospitalization will be summarized by treatment group. Two-sided 95% CIs for the observed difference in clinical events: death and hospitalizations between the treatment groups will be presented based on a continuity-correct Z-statistic. A by-subjects listing of subjects who died due to any cause will be provided.

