3.6.5 Cardiac Monitoring

Selected cardiac monitoring parameters will be summarized using descriptive statistics at baseline and Week 5 for the treatment group. Shifts from baseline to Week 5 will be presented for the clinical alert findings by treatment group and total.

All Cardiac monitoring data will be listed by subject.

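### Assigning visits by study day from the lead-in, with an open-ended Week 6 window and no rule for duplicate records, labels a Week 5 infusion visit held on Day 33 or after as Week 6.

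*SAP*

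**What the plan says.** - **Origin of the day count (SAP 3.1.1):** "Study day will be calculated from the date of first dose of study drug (lead-in infusion"), with that day as Day 1.
- **Assignment rule (SAP 3.1.3):** "Post-baseline assessments will be assigned a visit number based on the study day". Visits 2, 3 and 4 have windows of Days 2–11, 12–18 and 19–25. The last two are "Visit 5/Week 5/Day 29: Day 26 to Day 32, and" and "Visit 6/Week 6/Day 36: Day 33 or later". Section 3.1.3 does not say that the visit recorded in the eCRF is kept, and it does not say which record is used when two fall in one window.
- **Meaning of the weeks (SAP 2.2.1):** Weeks 2 to 5 are the blinded infusions, Week 4 is the planned titration step, and Week 6 is the evaluation visit.
- **Cardiac monitoring (SAP 2.3.4 and 3.6.5):** summarized at baseline and Week 5 only. "Shifts from baseline to Week 5 will be presented for the clinical alert findings by treatment group and total".
- **Functional class (SAP 3.4.2):** "will be summarized at each time point by treatment group as a shift table from baseline to post-baseline time point", and tested at Week 6 with a chi-squared test.
- **Vital signs (SAP 3.6.3):** summarized by visit and treatment group.

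**The concern.** The visits in this trial are a sequence of dosing steps, but the SAP labels them by calendar distance from the lead-in. If one infusion is given late and the later ones follow at weekly spacing, every later visit is displaced, and an assessment can be filed under a different dosing step from the one at which it was made. At the end of the sequence the open Week 6 window takes in both a late Week 5 infusion visit and the evaluation visit, and nothing in the SAP separates them.

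What is at stake is the Week 5 cardiac-monitoring summary, the by-visit safety tables and possibly the Week 6 functional-class test. With 36 randomized subjects planned, losing even a few collected records from a summary is noticeable.

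**Working it through.** **Inputs.** Target days (1, 8, 15, 22, 29, 36) and windows are from SAP 3.1.3. The delay patterns are illustrations, since the SAP gives none.

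**Step 1: the plan's own schedule.** On-time visits on Days 8, 15, 22, 29 and 36 fall in the windows for Weeks 2, 3, 4, 5 and 6. The rule reproduces its intended labels.

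**Step 2: when Week 5 becomes Week 6.** With a cumulative delay of s days, the Week 5 visit is on Day 29 + s. It is labelled Week 6 when 29 + s ≥ 33, that is, s ≥ 4.

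**Step 3: the windows applied to delayed sequences** (actual day → label assigned).

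| Pattern | Week 2 visit | Week 3 visit | Week 4 visit | Week 5 visit | Week 6 visit |
|---|---|---|---|---|---|
| On time | 8 → 2 | 15 → 3 | 22 → 4 | 29 → 5 | 36 → 6 |
| All 3 days late | 11 → 2 | 18 → 3 | 25 → 4 | 32 → 5 | 39 → 6 |
| All 4 days late | 12 → 3 | 19 → 4 | 26 → 5 | 33 → 6 | 40 → 6 |
| One day added per interval | 9 → 2 | 17 → 3 | 25 → 4 | 33 → 6 | 41 → 6 |
| One week lost before Week 2 | 15 → 3 | 22 → 4 | 29 → 5 | 36 → 6 | 43 → 6 |
| One week lost before Week 4 | 8 → 2 | 15 → 3 | 29 → 5 | 36 → 6 | 43 → 6 |

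Uniform shifts from 3 days early to 3 days late leave every label correct. From 4 days late there are two Week 6 records. With a uniform delay of 4 to 10 days, the Week 4 visit is also labelled Week 5. In the one-day-per-interval pattern no single interval is more than one day long, yet Week 5 still lands on Day 33.

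**Step 4: would the usual tie-break cure it?** Take the record closest to the Week 6 target, Day 36. Under a uniform delay s, the Week 5 visit is |29 + s − 36| = |s − 7| days away and the true Week 6 visit is s days away. The Week 5 visit is closer when |s − 7| < s, that is, s > 3.5. This covers every uniform whole-day delay that creates the duplicate (s ≥ 4). In the one-day-per-interval pattern the distances are 36 − 33 = 3 and 41 − 36 = 5, so the Week 5 record is again chosen. A tie-break added to the present windows would therefore tend to pick the wrong visit.

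**Step 5: which outputs are touched.**
- Cardiac monitoring: a record labelled Week 6 has no place in a baseline/Week 5 table, so it drops out. It remains in the by-subject listing.
- Vital signs by visit: values appear under the wrong dosing step.
- Functional class: if it is recorded at Week 5, two values compete for one Week 6 test.
- Exercise PCWP: if it is not measured at Week 5, a delayed subject still has only one Week 6 value.

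**The case against.** The strongest reply is that the problem is conditional and the SAP gives no sign of how often the condition arises. Visits within 3 days of target are labelled correctly, delayed visits may be brought back to target, and the permitted visit windows belong to the protocol. A record-selection rule may also sit in the separate programming specifications mentioned in SAP section 6. The point about frequency stands: any percentage of affected subjects would come from an assumed delay model, so none is given here. The point about the specifications helps less, because Step 4 shows that the usual rule makes the wrong choice while the labels stay as they are.

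Several stronger readings are tempting, but the document does not support them.

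- **That Week 5 cardiac monitoring is taken from the wrong visit.** It is planned only at baseline and Week 5, so a late record is lost from the summary and no other visit's value replaces it.
- **That the Week 6 functional-class test uses a Week 5 value.** This needs class to be recorded at Week 5, which the SAP does not show, and the earlier record to be the one chosen.
- **That the SAP itself expects infusion visits to be postponed.** Section 3.2.6 speaks of COVID-19 rescheduling only for the final visit, which the open window accommodates. The infusion change in section 5 concerns missed infusions.
- **That late infusions will be tabulated as missed.** Section 3.3.6 plans this: "A summary of subjects receiving the study drug will be provided by treatment assignments in the double-blind phase and in total for each visit". But the window rule covers assessments and does not say that infusion records are relabelled, and the same section counts infusions per subject whatever the visit label.
- **That Week 4 summaries mix infusion rates because of the windows.** Titration is conditional and rate reductions are allowed (section 2.2.1), so a mixture can arise in any case.

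**Conclusion.** The point holds as a conditional defect in a rule that the SAP states itself. Applied as written, section 3.1.3 mislabels the Week 5 infusion visit whenever it falls on Day 33 or after, and it leaves two Week 6 records with no way to choose between them.

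The certain consequence for such a subject is loss from the Week 5 cardiac-monitoring summary and shift table, together with wrong dosing-step labels in by-visit safety tables. The functional-class effect depends on an assessment schedule that is not shown. Delay is not expected to affect the primary PCWP analysis, on the assumption that exercise PCWP is not measured at Week 5. The number of subjects affected cannot be derived from the SAP. The point is worth correcting before database lock, but it does not put the trial's main conclusion at risk.

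**What to change.** Revise SAP section 3.1.3 to say that:

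- scheduled assessments are analysed under the visit recorded in the eCRF, where Weeks 2 to 5 are the planned blinded infusion visits and Week 6 is the evaluation visit after the last planned infusion;
- study-day windows are used only for unscheduled assessments, and early-termination assessments follow the combined Week 6/Early Termination grouping that section 3.6.4 already uses, where it applies;
- where several records fall in one visit, the scheduled record is used, and otherwise the one closest to the target day.

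Apply these labels to the cardiac-monitoring, functional-class, vital-signs and other by-visit tables. The order matters: the closest-to-target rule is safe only once scheduled records already carry their eCRF visit.

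The cost is SAP wording and a matching change to the programming specifications before database lock, with no new data. The small downside is that records under one label may come from somewhat different study days. Showing the study day in the listings would make this visible.

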3.2 Analysis Populations

3.2.1 Screened Set

The Screened Set is defined as subjects who signed informed consent.

3.2.2 Enrolled Set

The Enrolled Set is defined as subjects who signed informed consent and met open-label lead-in inclusion-enrollment criteria.

3.2.3 Randomized Set

The Randomized Set is defined as enrolled subjects who met all the inclusion-randomization criteria as responders to levosimendan for whom a randomization number was assigned.

3.2.4 Safety Analysis Set

The Safety Analysis Set is defined as enrolled/randomized subjects who received open-label levosimendan and/or any blinded study drug.

3.2.5 Full Analysis Set

The Full Analysis Set is defined as randomized subjects who received any blinded study drug and completed the study with Week 6 office visit.

3.2.6 Per-Protocol Set

The Per-Protocol Set is defined as subjects in the Full Analysis Set who completed the final scheduled primary assessment for the study and did not have pre-defined major protocol deviation.

Major protocol deviations may include but are not limited to:

- Did not meet recruitment inclusion criteria
- Did not complete the Week 6 office visit (or final office visit as rescheduled due to Coronavirus Disease 2019 [COVID-19])
- Missed more than one study drug infusion
- Did not have baseline and Week 6 (or final office visit as rescheduled due to COVID-19) data for primary endpoint

3.2.7 Pharmacokinetic Set

The Pharmacokinetic Set is defined as subjects in the Full Analysis Set for whom the primary pharmacokinetic data is considered sufficient and interpretable.

3.3 Subject Data and Study Conduct

3.3.1 Subject Disposition

Subjects in each analysis population, as well as subjects who complete the study, and subjects who prematurely discontinue from the study will be summarized by treatment assignments in the double-blind phase using descriptive statistics. In addition, for subjects who prematurely discontinue from the study, the reasons for discontinuation will be summarized by treatment group.

Subjects who discontinue the study prior to the Week 6 office visit will be replaced to ensure 18 randomized subjects in both arms (levosimendan, placebo) have completed the study for the primary analysis. If a subject has been identified for replacement, the Interactive Response Technology (IRT) will select the lowest available randomization number (with the same treatment group as the subject being selected) in the

"Replacement Blocks" section of the randomization schedule for the treatment assignment of the replacement subject. Thus, the treatment assignment of both the subject being replaced and the replacement subject will remain blinded.

3.3.2 Protocol Deviations

CSR reportable protocol deviations as defined in the Medpace Protocol Deviation Plan will be summarized for the Safety Analysis Set by treatment assignments in the double-blind phase and in total. The number and percentage of subjects with deviations will be summarized by deviation and overall.

A data listing of all CSR reportable protocol deviations will be provided by subject.

3.3.3 Demographic and Baseline Characteristics

The following demographic and baseline characteristics will be summarized:

- Age (years) and age categories (<65 years, ≥65 years)
- Sex
- Race
- Ethnicity
- Height (cm)
- Weight (kg)
- Body mass index (BMI) (kg/m²)
- Baseline hemodynamic parameters (PCWP, Cardiac Index, PVR, PAP (mean), RAP)
- Baseline echo measurements
- Baseline 6-Minute Walk Test (exercise distance) (m)

Demographic and baseline characteristics will be summarized with descriptive statistics or counts and percentages of subjects as appropriate by treatment assignments in the double-blind phase and in total for the Safety Analysis Set and Full Analysis Set.

